#### **6.7. Assessments for Premature Discontinuation from Study**

Discontinuation from study drug dosing and discontinuation from the overall study including follow-up will be collected as two separate events. If a subject discontinues study treatment dosing every attempt should be made to keep the subject in the study and continue to perform the required study-related follow-up and procedures (see Section [6.6](#)).

## 6.8. End of Study

Subjects are considered to have completed the study after the post-treatment Week 12 visit, regardless of treatment duration or early termination of study drug. If the subject terminates early due to HCV RNA  $\geq$  LLOQ, the subject may discontinue follow up after the post treatment Week 4 visit.

## 6.9. Procedures and Specifications

### 6.9.1. Central Laboratory Analytes

Hematology: Hematocrit, Hemoglobin (Hb), Platelet count, Red blood cell count (RBC), White blood cell count (WBC) with differential (absolute and percentage) including Lymphocytes, Monocytes, Neutrophils, Eosinophils, Basophils, Reticulocyte count and MCV.

Coagulation: INR, Prothrombin time (PT), Activated partial thromboplastin time (APTT).

Chemistry: Alanine aminotransferase (ALT/SGPT), Aspartate aminotransferase (AST/SGOT), Albumin, Alkaline phosphatase, Creatinine, Total Bilirubin (reflex Direct Bilirubin if Total is abnormal), Glucose, Lipase, Potassium, Sodium, and Gamma-glutamyl transferase (GGT). Creatinine clearance will be calculated based on the lesser of actual weight and ideal body weight.

Urinalysis: Blood, Glucose, Leukocyte esterase, pH, Protein, Urobilinogen. Reflex to microscopic urinalysis if dipstick result is abnormal.

Virological Tests: Serologies for HCV, HBV, and HIV. HCV RNA will be measured using the COBAS® AmpliPrep/COBAS® TaqMan® HCV Quantitative Test, version 2.0. HCV genotype and subtype will be determined using the Siemens VERSANT® HCV Genotype INNO-LiPA 2.0 Assay. Gilead reserves the right to use alternate assays for HCV RNA and HCV genotype should the above assays become unavailable or is not definitive.

IL28B genotype will be determined by polymerase chain reaction (PCR) amplification of the SNP, rs12979860, with sequence specific forward and reverse primers and allele specific fluorescently labeled TaqMan® MGB probes. Gilead reserves the rights to use an alternate assay for IL28B determination should the above assay become unavailable.

Pregnancy Tests: Serum  $\beta$ -hCG or Urine  $\beta$ -hCG (if positive, requires immediate confirmation with Serum  $\beta$ -hCG)

### 6.9.2. Medical History

Medical history including details regarding illnesses and allergies, date(s) of onset, and whether condition(s) is currently ongoing, and medication history will be collected on all subjects during screening up to the day of dosing. This will include information regarding the subject's HCV treatment history.

### 6.9.3. Complete Physical Examination

A complete physical examination must include source documentation of general appearance, and the following body systems: Head, neck and thyroid; eyes, ears, nose, throat, mouth and tongue; chest (excluding breasts); respiratory; cardiovascular; lymph nodes, abdomen; skin, hair, nails; musculoskeletal; neurological.

### 6.9.4. Vital Signs

Assessment of vital signs will include measurement of resting blood pressure, pulse, respiratory rate, and temperature.

Blood pressure will be measured using the following standardized process:

- Subject should sit for  $\geq 5$  minutes with feet flat on the floor and measurement arm supported so that the midpoint of the manometer cuff is at heart level;
- Use a mercury sphygmomanometer or automatic blood pressure device with an appropriately sized cuff with the bladder centered over the brachial artery;
- Measure and record the blood pressure to the nearest 2 mmHg mark on the manometer or to the nearest whole number on an automatic device.

### 6.9.5. MELD Score/Child-Pugh Score

MELD Score and Child-Pugh-Turcotte score should be assessed at Screening and on Day 1.

**Table 6-1. Child-Pugh-Turcotte Classification of the severity of cirrhosis**

	Points		
	1	2	3
Encephalopathy	None	Grade 1-2 (medication-controlled)	Grade 3-4 (medication-refractory)
Ascites	None	Mild/Moderate (diuretic-responsive)	Severe (diuretic-refractory)
Bilirubin (mg/dL)	< 2	2-3	> 3
Albumin (g/dL)	> 3.5	2.8-3.5	< 2.8
INR	< 1.7	1.7-2.3	> 2.3

Note: if the either ascites or encephalopathy is “none” because the patient is taking medication which has controlled the symptoms, the scoring should be 2 points (not 1 point).

CPT score is obtained by adding the points for each parameter

CPT class is scored as:  
 A = 5-6 points  
 B = 7-9 points  
 C = 10-15 points

## MELD Score Calculation

The MELD score is calculated as:

$$10 \times \{[0.957 \times \text{Ln}(\text{Scr})] + [0.378 \times \text{Ln}(\text{Tbil})] + [1.12 \times \text{Ln}(\text{INR})] + 0.643\}$$

Where Scr = serum creatinine (in mg/dL), Tbil = Total Bilirubin (in mg/dL), INR = international normalized ratio, and Ln = natural log. If any lab value is less than 1.0, then set to 1.0 in the calculation. If the subject received dialysis at least twice in the past week, then Scr is set to 4.0 mg/dL in the above formula. The result will be rounded to the nearest whole number.

For the components of the MELD score and the components of the CPT score which are based on laboratory values, the data will be obtained from the central laboratory, and the scores will be calculated within the clinical database.

### 6.9.6. Creatinine Clearance (CrCL)

Creatinine clearance is calculated by the Cockcroft-Gault equation {[Cockcroft et al 1976](#)}. Creatinine clearance will be calculated based on the lesser of actual weight and ideal body weight.

$$\text{Male: } \text{CL}_{\text{cr}} \text{ (mL/min)} = \frac{[140 - \text{age (years)}] \times \text{BW(kg)}}{72 \times S_{\text{cr}}}$$

$$\text{Female: } \text{CL}_{\text{cr}} \text{ (mL/min)} = \frac{[140 - \text{age (years)}] \times \text{BW(kg)} \times 0.85}{72 \times S_{\text{cr}}}$$

$S_{\text{cr}}$  = serum creatinine (mg/dL)

### 6.9.7. Ideal Body Weight (IBW)

Estimated ideal body weight in (kg)

Males: IBW = 50 kg + 2.3 kg for each inch over 5 feet.

Females: IBW = 45.5 kg + 2.3 kg for each inch over 5 feet

### 6.9.8. Body Mass Index (BMI)

BMI is calculated by the following equation.

$$\text{BMI} = \frac{\text{weight (pounds)} \times 703}{(\text{height in inches})^2} \quad \text{or} \quad \frac{\text{weight (kilograms)}}{(\text{height in meters})^2}$$

### **6.9.9. 12-Lead ECGs**

Subjects will be required to rest in a supine position for  $\geq 5$  minutes prior to making a recording.

The investigator (or qualified designee) should review the ECG traces recorded in real time for clinically significant abnormalities. On treatment ECGs should be compared to the subject's Day 1 as part of routine safety monitoring.

### **6.9.10. Pharmacokinetic (PK) Sample**

Single PK blood samples will be collected at each on-treatment visit for all subjects except on Days 1, 3 and 5. PK analysis of SOF (and its metabolites GS-566500 and GS-331007), and VEL may be conducted.

The exact date and time of the most recent dose of SOF/VEL taken prior to collection of the PK sample and the exact date and time the PK sample is drawn will be recorded on the appropriate eCRF.

All subjects will also be required to participate in an intensive PK sub-study (samples obtained over 24 hours) on Day 1 post-transplant. Serial PK samples will be collected at the following time points: 0 (pre-dose), 0.5, 1, 2, 4, 8, 12, and 24 hours post-dose. The PK of SOF, its metabolites GS-566500 and GS-331007, and VEL will be assessed.

Detailed regarding the collection, processing, and shipping of samples will be included in the lab manual.

### **6.9.11. Viral RNA Sequencing / Phenotyping Sample**

Plasma samples will be collected at Day 1 and at each visit for viral sequence analysis. At any unscheduled visit initiated for the purpose of confirming virologic breakthrough or relapse, a plasma sample for viral sequence analysis must be collected. Untested samples may be archived.

Details regarding the collection, processing, and shipping of samples will be included in the lab manual.

### **6.9.12. Pregnancy Testing**

All females of childbearing potential will have urine pregnancy testing at the Screening/pre-surgery visit, and Day 28 during the dosing period and for 30 days following the last dose of study drug. In the event of a positive urine pregnancy result, subjects will be instructed to stop study drugs immediately (if applicable) and return to the clinic as soon as possible for a serum pregnancy test.

## 7. ADVERSE EVENTS AND TOXICITY MANAGEMENT

### 7.1. Definitions of Adverse Events, Adverse Reactions, and Serious Adverse Events

#### 7.1.1. Adverse Events

An adverse event (AE) is any untoward medical occurrence in a clinical study subject administered a pharmaceutical medicinal product, which does not necessarily have a causal relationship with the treatment. An AE can therefore be any unfavorable and/or unintended sign, symptom, or disease temporally associated with the use of a medicinal product, whether or not considered related to the medicinal product. AEs may also include pre- or Post-treatment complications that occur as a result of protocol specified procedures, lack of efficacy, overdose, drug abuse/misuse reports, or occupational exposure. Preexisting events that increase in severity or change in nature during or as a consequence of participation in the clinical study will also be considered AEs.

An AE does not include the following:

- Medical or surgical procedures (eg, surgery, endoscopy, tooth extraction, transfusion) performed; the condition that led to the procedure may be an adverse event and must be reported.
- Pre-existing diseases, conditions, or laboratory abnormalities present or detected before the screening visit that do not worsen
- Situations where an untoward medical occurrence has not occurred (eg, hospitalization for elective surgery, social and/or convenience admissions)
- Overdose without clinical sequelae (see Section 7.6.1)
- Any medical condition or clinically significant laboratory abnormality with an onset date before the consent form is signed and not related to a protocol-associated procedure is not an AE. It is considered to be pre-existing and should be documented on the medical history CRF.

#### 7.1.2. Serious Adverse Events

A **serious adverse event** (SAE) is defined as an event that, at any dose, results in the following:

- Death
- Life-threatening (Note: The term “life-threatening” in the definition of “serious” refers to an event in which the subject was at risk of death at the time of the event; it does not refer to an event that hypothetically might have caused death if it were more severe.)
- In-patient hospitalization or prolongation of existing hospitalization

- Persistent or significant disability/incapacity
- A congenital anomaly/birth defect
- A medically important event or reaction: such events may not be immediately life-threatening or result in death or hospitalization but may jeopardize the subject or may require intervention to prevent one of the other outcomes constituting SAEs. Medical and scientific judgment must be exercised to determine whether such an event is a reportable under expedited reporting rules. Examples of medically important events include intensive treatment in an emergency room or at home for allergic bronchospasm; blood dyscrasias or convulsions that do not result in hospitalization; and development of drug dependency or drug abuse. For the avoidance of doubt, infections resulting from contaminated medicinal product will be considered a medically important event and subject to expedited reporting requirements.

### **7.1.3. Clinical Laboratory Abnormalities and Other Abnormal Assessments as Adverse Events or Serious Adverse Events**

Laboratory abnormalities without clinical significance are not recorded as AEs or SAEs. However, laboratory abnormalities (eg, clinical chemistry, hematology, and urinalysis) that require medical or surgical intervention or lead to IMP interruption, modification, or discontinuation must be recorded as an AE, as well as an SAE, if applicable. In addition, laboratory or other abnormal assessments (eg, electrocardiogram, x-rays, vital signs) that are associated with signs and/or symptoms must be recorded as an AE or SAE if they meet the definition of an AE or SAE as described in Sections 7.1.1 and 7.1.2. If the laboratory abnormality is part of a syndrome, record the syndrome or diagnosis (eg, anemia), not the laboratory result (ie, decreased hemoglobin).

## **7.2. Assessment of Adverse Events and Serious Adverse Events**

The investigator or qualified subinvestigator is responsible for assessing AEs and SAEs for causality and severity, and for final review and confirmation of accuracy of event information and assessments.

### **7.2.1. Assessment of Causality for Study Drugs and Procedures**

The investigator or qualified subinvestigator is responsible for assessing the relationship to IMP therapy using clinical judgment and the following considerations:

- **No:** Evidence exists that the adverse event has an etiology other than the IMP. For SAEs, an alternative causality must be provided (eg, pre-existing condition, underlying disease, intercurrent illness, or concomitant medication).
- **Yes:** There is reasonable possibility that the event may have been caused by the investigational medicinal product.

It should be emphasized that ineffective treatment should not be considered as causally related in the context of adverse event reporting.

The relationship to study procedures (eg, invasive procedures such as venipuncture or biopsy) should be assessed using the following considerations:

- **No:** Evidence exists that the AE has an etiology other than the study procedure.
- **Yes:** The AE occurred as a result of protocol procedures, (eg., venipuncture)

### **7.2.2. Assessment of Severity**

Severity should be recorded and graded according to the GSI Grading Scale for Severity of AEs and Laboratory Abnormalities ([Appendix 3](#)). For AEs associated with laboratory abnormalities, the event should be graded on the basis of the clinical severity in the context of the underlying conditions; this may or may not be in agreement with the grading of the laboratory abnormality.

### **7.3. Investigator Requirements and Instructions for Reporting Adverse Events and Serious Adverse Events to Gilead**

#### Requirements for collection prior to study drug initiation:

After informed consent, but prior to initiation of study medication, only those SAEs and adverse events related to protocol-mandated procedures should be reported on the case report form (eCRF).

#### Adverse Events

All AEs, except those described in Section 7.5, regardless of cause or relationship, that occur from initiation of study medication until 30-days after last administration of study drug must be reported to the eCRF database as instructed.

All AEs should be followed up until resolution or until the adverse event is stable, if possible. Gilead Sciences may request that certain AEs be followed beyond the protocol defined follow up period.

#### Serious Adverse Events

All SAEs, except those described in Section 7.5, regardless of cause or relationship, that occur from initiation of study medication until 30 days after last administration of study drug, must be reported to the eCRF database and Gilead Drug Safety and Public Health (DSPH) as instructed. This also includes any SAEs resulting from protocol-associated procedures performed after informed consent is signed.

Investigators are not obligated to actively seek SAEs after the protocol defined follow up period ;however, if the investigator learns of any SAEs that occur after study participation has

concluded and the event is deemed relevant to the use of IMP, he/she should promptly document and report the event to Gilead DSPH.

All AEs and SAEs will be recorded in the eCRF database within the timelines outlined in the eCRF completion guideline.

#### Electronic Serious Adverse Event (eSAE) Reporting Process

- Site personnel record all SAE data in the eCRF database and from there transmit the SAE information to Gilead DSPH within 24 hours of the investigator's knowledge of the event. Detailed instructions can be found in the eCRF completion guidelines.
- If for any reason it is not possible to record the SAE information electronically, ie, the eCRF database is not functioning, record the SAE on the paper serious adverse event reporting form and submit within 24 hours to:

Gilead DSPH	Email:	[contact]
	[contact]

Gilead Medical Monitor	Name:	[name]
	Phone:	PPD PPD
	Fax:	PPD
	Email:	PPD

- As soon as it is possible to do so, any SAE reported via paper must be transcribed into the eCRF Database according to instructions in the eCRF completion guidelines.
- If an SAE has been reported via a paper form because the eCRF database has been locked, no further action is necessary.
- For fatal or life-threatening events, copies of hospital case reports, autopsy reports, and other documents are also to be submitted by e-mail or fax when requested and applicable. Transmission of such documents should occur without personal subject identification, maintaining the traceability of a document to the subject identifiers.
- Additional information may be requested to ensure the timely completion of accurate safety reports.
- Any medications necessary for treatment of the SAE must be recorded onto the concomitant medication section of the subject's eCRF and the event description section of the SAE form.

#### **7.4. Gilead Reporting Requirements**

Depending on relevant local legislation or regulations, including the applicable US FDA Code of Federal Regulations, the EU Clinical Trials Directive (2001/20/EC) and relevant updates, and other country-specific legislation or regulations, Gilead may be required to expedite to

worldwide regulatory agencies reports of SAEs, serious adverse drug reactions (SADRs), or suspected unexpected serious adverse reactions (SUSARs). In accordance with the EU Clinical Trials Directive (2001/20/EC), Gilead or a specified designee will notify worldwide regulatory agencies and the relevant IEC in concerned Member States of applicable SUSARs as outlined in current regulations.

Assessment of expectedness for SAEs will be determined by Gilead using reference safety information specified in the investigator's brochure or relevant local label as applicable.

All investigators will receive a safety letter notifying them of relevant SUSAR reports associated with any study IMP. The investigator should notify the IRB or IEC of SUSAR reports as soon as is practical, where this is required by local regulatory agencies, and in accordance with the local institutional policy.

## **7.5. Reporting Requirements for Liver Transplant and Complications of Liver Transplant**

Due to the nature of the subject population and the inclusion criteria, events that are clearly related to liver transplant should not be collected or reported as AEs and SAEs. In addition, these events will be exempt from global expedited reporting requirements for the duration of the study. These include:

- 1) The liver transplant procedure itself (and related hospitalization)
- 2) Events that are direct sequelae of the liver transplant or peri-operative care (central line insertions, etc)
- 3) Planned hospitalizations for testing or procedures that are part of the liver transplant assessment and preparation process

These events should be reported as AEs/SAEs only if it is assessed that the events (including transplant itself) were not an anticipated or predictable part of the underlying disease transplant process or procedure. Events that are considered possibly or probably related to study medication must be reported using the usual reporting procedures, as described in Section 7.3. In addition, concomitant medications related to the transplant procedure do not need to be recorded (anesthetics, peri-operative pain medication, etc). If there are any questions about how an event should be reported, please contact the study Medical Monitor.

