**Criteria for Evaluation:**

**Safety:** AEs and safety laboratory tests will be collected throughout the study (through the Post-treatment week 4 visit).

**Efficacy:** Efficacy will be evaluated using scheduled assessments of HCV RNA performed using Roche COBAS® AmpliPrep/COBAS® TaqMan® HCV Test, v. 2.0.

**Pharmacokinetics:** A single PK blood sample will be collected at each on-treatment visit for all subjects except on Days 1, 3 and 5.

All subjects will be required to participate in an intensive serial PK sub-study to be performed on Day 1. The PK of SOF (and its metabolites GS-566500 and GS-331007), and VEL will be assessed. Serial PK samples will be collected at the following time points: 0 (pre-dose), 0.5, 1, 2, 4, 8, 12 and 24 hours post-dose.

---

---

**Statistical Methods:** The primary efficacy endpoint is the percentage of subjects who achieve SVR12 (HCV RNA < lower limit of quantitation [LLOQ] 12 weeks after stopping study drug) for subjects in the Full Analysis Set (FAS).

Secondary efficacy endpoints include the percentage of subjects who attain SVR at 4 weeks after cessation of treatment (SVR4); the percentage of subjects who have HCV RNA <LLOQ at each on-treatment visit; and the percentage of subjects with virologic failure (VF, defined as HCV RNA  $\geq$  LLOQ at end of treatment or relapse during the Post-treatment follow-up period).

The primary safety endpoint is the percentage of subjects who discontinue from study drug due to an adverse event. Deaths, graft loss, and rejection episodes will also be listed or summarized, as appropriate.

Other endpoints of interest include changes to immunosuppressive therapy and the emergence of viral resistance to SOF or VEL during and after cessation of treatment, and HCV RNA levels (IU/mL) at each on-treatment visit, if relevant.

---

This study will be conducted in accordance with the guidelines of Good Clinical Practice (GCP) including archiving of essential documents.

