### **3.5. Discontinuation Criteria**

When medically feasible, the Medical Monitor must be consulted prior to subject discontinuation.

Study drug must be discontinued in the following instances:

- Unacceptable toxicity, as defined in Section 7.6 of the protocol, or toxicity that, in the judgment of the investigator, compromises the ability to continue study-specific procedures or is considered to not be in the subject's best interest
- If a subject experiences graft dysfunction (including primary graft non-function) requiring relisting for liver transplant, treatment will be stopped
- If subject is relisted for transplantation for any reason treatment will be stopped
- Subject receives a 2nd liver transplant while on study treatment
- Pregnancy of female subject
- Significant protocol violation
- Subject request to discontinue for any reason; it is important to determine whether the withdrawal of consent is primarily due to an AE, lack of efficacy, or other reason
- Discontinuation of the study at the request of Gilead, regulatory agency, or an Institutional Review Board (IRB)/Independent Ethics Committee (IEC)

If a subject meets discontinuation criteria during treatment, an Early Termination visit will be required (Section 6.4) Subjects who permanently discontinue all study drugs for any reason including safety and/or tolerability concerns prior to completion of the assigned dosing period will be followed according to the Post-treatment study assessments to determine whether the subject achieves SVR.

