### **3.6. Subject Stopping Rules**

The Gilead Medical Monitor must be consulted prior to discontinuation of study drug unless the investigator believes that immediate action is warranted to ensure the continued safety of the subject.

Administration of study medication may be discontinued due to a clinical or laboratory event. There is no option for SOF/VEL dose reduction. If SOF/VEL is stopped due to toxicity, it must

not be restarted and the subject must complete an ET visit. Any interruptions of study medication must be discussed with the Sponsor Medical Monitor prior to restarting.

Subjects who meet any of the following laboratory or medical criteria must stop all study medication(s):

- Any medical condition (in the opinion of the Medical Monitor) for which the risks of treatment outweigh the benefits
- Commencement of dialysis
- Any Grade 3 or greater rash associated with constitutional symptoms
- Any Grade 4 adverse event assessed as related to SOF/VEL

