### **8.1.4. Safety Endpoint**

The primary safety endpoint is any AE leading to premature discontinuation of study drug. Other important safety endpoints include deaths, graft losses, and rejection episodes.

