7.1.6. Summaries of Adverse Events and Deaths

A brief high-level summary of TEAEs will be provided for the SOF/VEL 4 Week group. The number and percentage of subjects who had the following: any AE; any treatment-related AE; any AE of Grade 3 or above; any treatment-related AE of Grade 3 or above; any AE of Grade 2 or above; any treatment-related AE of Grade 2 or above; any SAE; any treatment-related SAE; any AE leading to premature discontinuation of SOF/VEL; and any AE leading to interruption of SOF/VEL. All deaths (including those that are treatment-emergent and those that are not treatment-emergent) observed during the study will also be summarized and included in this table.

Adverse event summaries will provide the number and percentage of subjects with TEAEs by SOC and PT for the SOF/VEL 4 Week group based on the the Safety Analysis Set as follows:

- All AEs
- All treatment-related AEs
- AEs of Grade 3 or above
- Treatment-related AEs of Grade 3 or above
- AEs of Grade 2 or above
- Treatment-related AEs of Grade 2 or above
- All SAEs
- Treatment-Emergent Non-Serious Adverse Events Occurring in At Least 5% of Subjects

Multiple events will be counted once only per subject in each summary. Adverse events will be summarized and listed first in alphabetic order of SOC and then by PT in order of descending incidence within an SOC. In summaries by severity grade, the most severe grade will be used for those AEs that occurred more than once in an individual subject during the study.

In addition to the above summary tables, TEAEs will also be summarized for the SOF/VEL 4 Week treatment group by PT only, in order of descending incidence for:

- AEs that occurred in > 1 subject
- AEs leading to interruption of SOF/VEL
- AEs leading to premature discontinuation of SOF/VEL
- All SAEs
- All treatment-related SAEs

In addition to the by-treatment summaries described above, by-subject data listings, with a variable indicating whether the event is treatment-emergent, will be provided for the following:

- All AEs
- AEs leading to premature discontinuation of SOF/VEL
- All AEs of Grade 3 or above
- SAEs
- All Deaths
- Graft Loss

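### A stop of SOF/VEL that the protocol requires can be missing from the primary safety endpoint, because Section 7.5 exempts transplant-related events from AE collection without an exception for events that stop the drug

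*Protocol*

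**What the plan says.** **The endpoint.** Protocol 8.1.4: "The primary safety endpoint is any AE leading to premature discontinuation of study drug". The synopsis puts it per subject: "The primary safety endpoint is the percentage of subjects who discontinue from study drug due to an adverse event". SAP 7.1.6 reports it through the summary and listing of "AEs leading to premature discontinuation of SOF/VEL" (Tables 15 and 24, Listing 10).

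**The exemption.** Protocol 7.5: "events that are clearly related to liver transplant should not be collected or reported as AEs and SAEs". One of its three categories reads "Events that are direct sequelae of the liver transplant or peri-operative care (central line insertions, etc". Two conditions bring an event back into collection: it was not an expected part of the transplant process, or it may be related to study drug. Protocol 7.3 defers to this section: it requires reporting of "All AEs, except those described in Section 7.5, regardless of cause or relationship", and the SAE paragraph has the same exception.

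**The required stops.** Protocol 3.5: "If a subject experiences graft dysfunction (including primary graft non-function) requiring relisting for liver transplant, treatment will be stopped". It also requires a stop for relisting for any reason and for a second transplant during treatment. Protocol 3.6 adds "Commencement of dialysis".

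**Rules that point the other way.** Protocol 7.1.1 says a procedure is not itself an AE, but the condition behind it may be one and must then be reported. Protocol 7.1.3 requires an AE record for a laboratory abnormality that needs intervention or leads to discontinuation of study drug.

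**The concern.** The endpoint can count a stop only if an AE was recorded for it. Section 7.5 decides which events are recorded, and it does so on cause and predictability. It never asks whether the event ended treatment. Everywhere else, 7.3 collects AEs whatever their cause, so 7.5 puts a cause judgment ahead of recording.

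This matters because a primary objective is safety in the peri-operative and post-transplant period. Dosing starts on the day of transplant or the day after (with up to one further day's delay) and lasts four weeks, so treatment coincides with the time when transplant sequelae occur. Patients on hemodialysis before or at transplant are excluded, so dialysis starting on study would be new. If such a stop is not recorded as an AE, a reader of the primary safety result cannot tell a true 0% from a 0% produced by the recording rule.

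**Working it through.** **1. Can a required stop lack an AE record?**

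| Step | Source | Result |
|---|---|---|
| Drug must stop for graft dysfunction with relisting, relisting, second transplant, dialysis | Protocol 3.5, 3.6 | Stop is mandatory |
| Event judged clearly related to transplant and a direct sequela | Protocol 7.5 | Exempt from AE/SAE collection |
| Exception: not anticipated or predictable | Protocol 7.5 | Does not apply if the investigator judges it anticipated |
| Exception: possibly or probably drug-related | Protocol 7.5 | Does not apply if judged unrelated |
| Exception: event stopped the drug | None in 7.5 or 7.3 | No route back |
| Treatment-emergent definition includes AEs leading to discontinuation | SAP 7.1.5.1 | Classifies recorded AEs only; cannot recover an unrecorded one |
| Endpoint tables and listing | SAP 7.1.6; Tables 15 and 24; Listing 10 | Stop not counted |

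The path is open, and it depends on two investigator judgments. SAP 7.8 reports no departure from the protocol's safety analyses, so the SAP does not close it.

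**2. How many of the stopping criteria are involved?** Section 3.5 lists eight and 3.6 lists four, 8 + 4 = 12. Four fit the path above. Three of those four (graft dysfunction with relisting, relisting, second transplant) largely describe one clinical course.

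**3. The plan's own precision figure.** Protocol 8.8 and SAP 1.3 give a maximum exact 95% CI length of 63% for n = 10. The Clopper-Pearson limits for x events in n are

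- lower = Beta quantile (0.025; x, n − x + 1), with 0 if x = 0
- upper = Beta quantile (0.975; x + 1, n − x), with 1 if x = n

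The interval is widest at x = 5: 18.7% to 81.3%, length 62.6%, which rounds to 63%. The figure reproduces.

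**4. Size per uncounted stop.** 1/10 = 10 percentage points. The documents give no rate for these stops, so the counts below are assumptions, with no other AE-related stop in the study.

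| Exempt stops (assumed) | Endpoint if not recorded | Endpoint if counted |
|---|---|---|
| 0 | 0/10 = 0% (0% to 30.8%) | 0/10 = 0% (0% to 30.8%) |
| 1 | 0/10 = 0% (0% to 30.8%) | 1/10 = 10% (0.3% to 44.5%) |
| 2 | 0/10 = 0% (0% to 30.8%) | 2/10 = 20% (2.5% to 55.6%) |

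Two limits can be checked by hand: the upper limit for 0/10 is 1 − 0.025^(1/10) = 30.8%, and the lower limit for 1/10 is 1 − 0.975^(1/10) = 0.3%.

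**5. Chance that the question arises at all.** For an assumed per-subject risk p of such a stop, P(at least one in 10) = 1 − (1 − p)^10. This gives 40% at p = 5%, 65% at 10%, 89% at 20% and 97% at 30%.

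**The case against.** The strongest reply is that the overlap between 7.5 and the stopping criteria is an inference. Section 7.5 names none of graft dysfunction, relisting, second transplant or dialysis; its examples are the transplant and its hospitalization, line insertions and planned admissions. An event escapes recording only if it is clearly transplant-related, anticipated, and not possibly drug-related. The causality rule in 7.2.1 asks for evidence of another cause before the answer is No, so doubtful cases lean towards being reported. Renal failure leading to dialysis would usually bring laboratory abnormalities that 7.1.3 says to record. The Medical Monitor is normally consulted before a stop and answers reporting questions under 7.5. With 10 subjects every stop is visible individually: SAP 4.1.3 gives reasons for not completing treatment, deaths and graft loss are listed (Listings 13.1 and 13.2), and the DMC receives premature discontinuations.

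Most of this stands, and it rules out three stronger readings that a reader might infer:

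- That a site following 7.5 must record no AE. The section permits that outcome after two judgments; it does not require it.
- That the mandatory stops are mainly transplant events. Four of twelve criteria are.
- That the stops vanish from the report, or that the endpoint is shown to be biased towards zero. The stops remain in disposition, and no rate is available from which to show a bias.

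The reply does not close the gap. Neither 7.1.1 nor 7.1.3 is said to override 7.5, and 7.3 gives way to 7.5 by name. Section 7.5 speaks of possible or probable relatedness while 7.2.1 offers only Yes or No, so the threshold for reporting is itself unclear. Disposition and the listings are not the primary safety endpoint.

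**Conclusion.** The point holds as a gap in a recording rule. A stop that 3.5 or 3.6 requires, judged an anticipated transplant sequela and unrelated to drug, may have no AE record and so may be absent from the primary safety endpoint. Each such stop lowers the endpoint by 10 percentage points with 10 subjects; one stop would read 0/10 (0% to 30.8%) instead of 1/10 (0.3% to 44.5%).

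This rests on two assumptions: that at least one such stop occurs, and that the investigator makes both judgments in the direction that exempts it. The documents settle neither. The case for acting is that the primary safety result is open to understatement by an avoidable rule, and that the remedy is small.

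**What to change.** **Protocol 7.5.** Add a sentence stating that the exemption from AE collection does not apply to any event leading to interruption or permanent discontinuation of SOF/VEL. The exemption from expedited reporting can stay. Reconcile 7.1.1, 7.1.3, 7.3 and 7.5 so that the order of precedence is explicit.

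**SAP 7.1.6, Tables 15 and 24.** Beside the AE-based endpoint, add a row counting all premature stops for a medical reason, by cause: AE, graft dysfunction or relisting, second transplant, dialysis. It can be built from the disposition reasons already planned in SAP 4.1.3. SAP 3.1.2 speaks of enrolled subjects as already transplanted and dosed, so the protocol sentence may come late for some of them; the SAP row works even if enrolment is complete. The documents do not list the reason categories, so it should be checked that they separate these causes; with about 10 subjects, any that do not can be resolved case by case.

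**Cost.** One sentence, one table row and a few more AE records, some possibly retrospective. The reported discontinuation rate may look less favourable. No stopping rule changes.
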